11.3 Clinical Laboratory Evaluations

The following hematology and serum biochemistry central laboratory tests will be summarized by visit and by treatment group. The summaries will be provided for the analysis population (Safety Analysis Set) as described in [Section 11](#). Data for urinalysis will only be listed.

Hematology: Hematocrit, hemoglobin, platelet count, reticulocytes, erythrocytes (red blood cell count [RBC]) count, RBC indices of mean corpuscular hemoglobin concentration (MCHC); mean corpuscular hemoglobin (MCH); mean corpuscular volume (MCV); red cell (erythrocyte) distribution width (RDW), leukocyte (white blood cell count [WBC]) counts, differential (absolute and percentage) of neutrophils; neutrophil band forms, lymphocytes, monocytes, eosinophils, and basophils.

Serum Biochemistry: Sodium, potassium, chloride, bicarbonate, calcium, blood urea nitrogen (BUN), urea, creatinine, glucose, protein, albumin, alkaline phosphatase, alanine aminotransferase (ALT), aspartate aminotransferase (AST), lactate dehydrogenase (LDH), gamma-glutamyl-transferase (GGT), bilirubin (total), bilirubin (direct), magnesium, phosphate, high sensitivity-C reactive protein (hs-CRP), cholesterol, high-density Lipoprotein (HDL) cholesterol, low-density lipoprotein (LDL) cholesterol, triglycerides, urate (uric acid), creatine kinase / creatine phosphokinase (CK / CPK), activated partial thromboplastin time (aPTT), prothrombin time (PT) / international normalized ratio (PT / INR), pF1+2, fibrinogen (Clauss assay), D-dimer.

Urinalysis: Specific gravity, pH, occult blood, leukocyte esterase, nitrite, erythrocytes, ketones, bilirubin, protein, urobilinogen, glucose.

Standard safety laboratory data from central lab will be presented in international system of units (SI units) and in the order presented as above given. Measured laboratory values will be summarized descriptively by scheduled visit. Changes from baseline for laboratory parameter will be derived and presented in the same way as measured laboratory values.

A laboratory value that is outside the reference range is either high abnormal (value above the upper limit of the normal [ULN] reference range) or low abnormal (value below the lower limit of the normal [LLN] reference range). An abnormal laboratory value is not necessarily of potential clinical interest. For each of the hematology and serum biochemistry lab tests, shift tables will be constructed to compare the individual subject baseline value with respect to the normal range to their Day 92 (or last observed value prior to Day 92 in case of dropouts or missing assessment at Day 92) value with respect to the normal range.

The denominator in percentage calculation at a scheduled visit will be based on the number of subjects with a non missing value at that particular visit. The definition of the baseline assessment is given in [Section 8.2.3](#).

A by-subject listing of all laboratory values including flag for values out of normal range will be provided. By-subject listing will include in general all visits (scheduled and unscheduled).

Immunogenicity:

The number and percentage of subjects with a positive immunogenicity test (presence of binding antibodies to CSL312) at any time and separate for Day 36 and Day 92 during treatment will be summarized by treatment group for the analysis population (Safety Analysis Set) as described in [Section 11](#).

A by-subject listing for immunogenicity will be provided.

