The primary endpoints of this study are subjects experiencing TEAEs including SAEs, AESIs, CSL312-induced ADAs, and clinically significant abnormalities in laboratory assessments that are reported as AEs. The summary measures will be the number and proportion of subjects experiencing these safety events after treatment with investigational product (CSL312 or placebo).

TEAEs will be summarized by the number and percentages of subjects experiencing ≥ 1 TEAE and the number of events. TEAEs will be summarized by system organ class and preferred term and also by causality and severity.

More detailed information on the analyses of efficacy, safety, PK, PD, and biomarkers are provided in the full clinical study protocol.

Schedule of Assessments

Study Period		Screening/ Washout Period ^A	Treatment and Observation Period											FU Visit (Phone Call) ^B		
			1	2	3	6	7	10	11	12	13	EOT/EW 14 ^C	22			
Study Week	-4	1	2	3	6	7	10	11	12	13	EOT/EW 14 ^C	22				
Study Day	-28	1	8	15	36	43	64	67	71	78	85	92	154			
Time (Hours) ^D		Baseline Predose	0	EOP ^D												
Visit Window (Days)					±1	±1	±2	±1	±1	±1	±1	±2	±2	±2	±5	
Informed consent ^E		X														
Inclusion / exclusion criteria		X	X													
Medical history and demographics		X														
Randomization via IRT			X													
Treatment assignment via IRT			X		X		X		X							
Administration of investigational product				IV	SC		SC		SC							
12-lead ECG		X	X		X		X		X					X		
Pregnancy test ^F		X	X		X		X		X					X		
Physical examination		X	X		X		X		X					X		
Vital signs ^G		X	X		X		X		X					X		
Urine sample for urinalysis (central laboratory)		X	X		X		X		X					X		
Blood Samples (central laboratory)	Hematology ^H , biochemistry ^{I,J} , and coagulation ^K	X	X		X		X		X					X		
	Retention sample for virology ^L		X													
	PD and biomarkers ^{M,N,O}	X ^N	X ^{M,N,O}		X ^O	X ^{M,N,O}	X ^O	X ^{M,N,O}	X ^O	X ^{M,N,O}	X ^O	X ^O	X ^O	X ^O	X ^{N,O}	
	PK		X ^M		X	X ^M	X	X ^M	X	X ^M	X	X	X	X	X	
RNA Seq / proteomics		X	X ^M		X ^M		X ^M		X ^M					X		
INR and D-dimer (local laboratory)		X	X													
Immunogenicity (ADAs; central laboratory) ^P			X				X							X		
Spirometry at site (local laboratory) ^Q		X	X		X		X		X					X		
DL _{CO} (local laboratory) ^Q		X	X											X		
AEs ^R																
Prior / concomitant therapies ^R																

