1.4.2 Potential Risks

Potential risks associated with CSL312 have been considered based on the anticipated effects of the proposed mechanism of action and known risks associated with drugs of the same or similar class. The following events constitute potentially important medical risks:

- **Severe hypersensitivity including anaphylaxis:** Administration of therapeutic proteins including monoclonal antibodies such as CSL312 may be associated with the risk of hypersensitivity and anaphylactic reactions, some of which can be serious and life-threatening. To date, no severe hypersensitivity or anaphylactic-type reactions have been observed after repeated administration of CSL312 in the completed or ongoing clinical studies. Nevertheless, administration of CSL312 will be performed at the study site under medical supervision, with immediate access to emergency equipment and medication for the treatment of severe hypersensitivity, including anaphylaxis. Subjects will be informed of the early signs of hypersensitivity reactions including hives, generalized urticaria, tightness of the chest, wheezing, hypotension, and anaphylaxis, and will be encouraged to report any symptoms to site personnel.
- **Abnormal bleeding and thromboembolic events:** By blocking FXIIa, CSL312 may be associated with a potential risk of bleeding or TEEs, due to altered hemostasis, unstable clot formation, or impaired clot breakdown. In addition, due to the pharmacological action of CSL312, a concentration-dependent prolongation of aPTT was observed with dosages similar to those proposed in this study. Clinical experience with CSL312 in study CSL312_1001 and CSL312_2001 did not show an effect on prothrombin time (PT). This is consistent with the observation that patients who have a congenital deficiency of FXII do not exhibit a bleeding phenotype, despite having a prolonged aPTT [[Lammle et al, 1991](#); [Ratnoff and Colopy, 1955](#)]. In addition, nonclinical studies in mice and rabbits showed no impairment in hemostasis after inhibition of FXIIa [[Larsson et al, 2014](#)]. Nevertheless, subjects will be monitored carefully for any signs of thrombosis or bleeding during the study.

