10.3.3 Safety Analyses

TEAEs will be coded using the Medical Dictionary for Regulatory Activities (MedDRA) version 24.1 (or higher). A TEAE is defined as an AE reported at or after the start of the first administration of study treatment. Only TEAEs will be summarized.

An overview summary of TEAEs, including counts and percentages of subjects with any of the following events, will be produced:

- TEAEs
- TEAEs related to study treatment
- TEAEs leading to permanent discontinuation of study treatment
- Serious TEAEs
- Serious TEAEs related to study treatment
- Fatal TEAEs

- Fatal TEAEs related to study treatment
- TEAEs by severity
- Treatment-emergent AESIs

TEAEs will be summarized by system organ class and preferred term. TEAEs will also be summarized by causality and severity. All TEAE summaries will be provided for each treatment group and overall.

The number and percentage of subjects with plasma anti-CSL312 antibodies will be summarized by treatment group and overall.

Laboratory evaluations (hematology, biochemistry, and urinalysis) will be summarized descriptively by treatment group.

Change from Baseline in DL_{CO} will be summarized using descriptive statistics by treatment group.

The Safety Analysis Set will be used for the safety analyses unless indicated otherwise.

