4.5.1 Independent Data Monitoring Committee

The roles and responsibilities of the independent data monitoring committee (IDMC) and the safety data review schedules are described in the IDMC charter. Operationally, since the IDMC is ad-hoc and can be triggered before SAS programming can be done to generate summary output, in this case, only data dump listings will be generated. Otherwise, those summary tables will be provided for the following (along with their supporting listings):

- Demographics;
- Treatment and exposure;
- AE overall summary, SAEs, AEs, AESIs.

Other safety analysis output as listed below, will be provided as data listings:

- Vital signs, physical exams and respiratory tests;
- Safety laboratory parameters / urinalysis;
- ECG;
- Medical history;
- Concomitant medication;
- Spirometry.

Please refer to [Sections 9, 10, and 11](#) of this SAP for descriptions of the analysis listed above.

5 Changes from the Protocol Planned Analyses

There are no changes to the planned analyses as previously documented in the CSP.

The definition of screened analysis set was slightly modified, please refer to Section 6.1.

6 Study Analysis Sets

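### SAP 11.3 reduces urinalysis to a by-subject listing, although Protocol 10.3.3 calls for a descriptive summary by arm, and SAP Section 5 does not declare the change

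*SAP*

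**What the plan says.** Protocol 10.3.3 (Safety Analyses) states: "Laboratory evaluations (hematology, biochemistry, and urinalysis) will be summarized descriptively by treatment group". Urinalysis is named expressly.

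SAP 11.3 (Clinical Laboratory Evaluations) opens with a narrower scope: "The following hematology and serum biochemistry central laboratory tests will be summarized by visit and by treatment group". On urine it then says: "Data for urinalysis will only be listed". The shift tables have the same limit: "For each of the hematology and serum biochemistry lab tests, shift tables will be constructed". The urinalysis panel in that section is: "Specific gravity, pH, occult blood, leukocyte esterase, nitrite, erythrocytes, ketones, bilirubin, protein, urobilinogen, glucose".

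SAP Section 5, where departures from the protocol belong, states: "There are no changes to the planned analyses as previously documented in the CSP". The only modification it goes on to mention is the definition of the Screened Analysis Set.

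**The concern.** The two documents give opposite instructions for the same data, and the SAP does not acknowledge it. The declaration in SAP Section 5 shows that even a slight change to an analysis set was thought worth recording, so silence on urinalysis looks like an oversight rather than a decision. It may also stay hidden. SAP Section 3 says the study report will detail deviations from the SAP, and a listing-only output complies with the SAP.

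Safety is the primary objective, and two of the urine tests detect blood. Protocol 1.4.2 names abnormal bleeding among the potential risks and says that "subjects will be monitored carefully for any signs of thrombosis or bleeding during the study". Abnormal bleeding is also an adverse event of special interest (Protocol 9.1.3). Protocol 3.9.2 recognizes that events which look minor one at a time can together be a safety concern. A difference of that kind between arms is easy to see in a table of counts and hard to see in a by-subject listing.

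**Working it through.** This is a comparison of texts; the plan attaches no figure to urinalysis.

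**Step 1. Set the instructions side by side.**

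| Laboratory group | Protocol 10.3.3 | SAP 11.3 by-arm summary | SAP 11.3 shift table | SAP 11.3 listing |
|---|---|---|---|---|
| Hematology | Summary by arm | Yes | Yes | Yes |
| Biochemistry (the SAP list also holds the coagulation tests) | Summary by arm | Yes | Yes | Yes |
| Urinalysis | Summary by arm | No | No | Yes |

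Only the urinalysis row disagrees.

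**Step 2. Look for another output that restores the summary.**

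- SAP 11.3 also says in general terms that measured laboratory values are summarized by scheduled visit. The specific sentence on urinalysis in the same section overrides this.
- The data monitoring package in SAP 4.5.1 gives urinalysis as a data listing.
- SAP Section 5 declares no change on this point.

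None of these fills the gap.

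**Step 3. Find which urine results still reach a by-arm table.** Under Protocol 9.1.1, a laboratory value that the investigator considers clinically significant must be recorded as an adverse event. Changes or trends within the reference range may also be recorded at the investigator's discretion. SAP 11.2 tabulates treatment-emergent events by arm. The results left out are therefore those the investigator does not judge clinically significant and does not record as events.

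**Step 4. Check document versions.** SAP Section 3 lists protocol versions up to Amendment 2, and the protocol supplied is Amendment 3. The Amendment 3 change list names no change to 10.3.3, although it includes a general item for minor corrections. The Amendment 2 text is not available to confirm this. If the wording did change, the SAP would still need to be brought into line with the current protocol.

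**Step 5. Scale.**

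- Subjects: 80 enrolled for 70 evaluable at 12% dropout (Protocol 10.1). This reproduces: 70 / (1 − 0.12) = 79.5, rounded up to 80.
- Post-dose urinalysis visits: 4. The urinalysis row of the Schedule of Assessments has six marks, read as Screening, Day 1 predose and Days 8, 36, 64 and 92. This is a reading, because the extracted table is broken.
- Results per urine parameter: 80 × 4 = 320, or 70 × 4 = 280 for the evaluable number.
- Occult blood plus erythrocytes: 80 × 4 × 2 = 640, or 70 × 4 × 2 = 560.
- Whole panel of 11 parameters: 80 × 4 × 11 = 3,520, or 70 × 4 × 11 = 3,080. This includes items such as pH, ketones and specific gravity, which do not bear on bleeding.

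These count all results that would be listed, normal or abnormal. The documents give no expected rate of positive urine tests, so the size of any missed imbalance cannot be stated.

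**The case against.** The strongest reply is that this is a consistency error with little effect on the safety assessment. Much of that stands.

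- A reader might infer that blood in the urine is never compared between arms. That is too strong, because findings judged clinically significant are adverse events and are tabulated by arm. SAP 11.2 also identifies bleeding events of special interest by the narrow Haemorrhages query, so an event coded there counts whether or not the investigator called the bleeding abnormal.
- A reader might infer that all other evidence of bleeding depends on subject report or investigator judgment. It does not. SAP 11.3 summarizes hemoglobin, hematocrit, red cell count, reticulocytes, platelets, aPTT, PT/INR, fibrinogen and D-dimer by visit and arm, and gives them shift tables.
- A reader might infer that part of the primary endpoint is lost. Protocol 2.1.2 limits its laboratory component to abnormalities reported as adverse events. Dipstick changes that are not adverse events fall outside it.
- A reader might treat urinalysis as the trial's bleeding monitor. Protocol 1.4.2 names severe hypersensitivity, bleeding and thromboembolic events, and immunogenicity, and nowhere gives urinalysis that role. Bleeding experience so far is also reassuring: none in the completed healthy-volunteer study, and in the COVID-19 study four bleeding events of special interest, all in one placebo subject.

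The listing also flags out-of-range values, which makes it easier to read. What the reply does not remove is the contradiction. The protocol promises a summary by arm, the SAP withdraws it, and no reason is given.

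**Conclusion.** The point holds as an undeclared departure of the SAP from the protocol. The contradiction is certain on the text supplied; its consequence is modest. Urinalysis results that the investigator does not judge clinically significant appear in no by-arm table. For occult blood and erythrocytes this concerns roughly 560 to 640 post-dose results, most of which may be normal. The range assumes four post-dose urinalysis visits and complete attendance by 70 to 80 subjects.

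The documents do not support the stronger reading that the trial has no by-arm laboratory evidence on bleeding, or that a primary endpoint analysis is missing. The reason to act is that the protocol's commitment should be kept, or openly changed, and keeping it is cheap.

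**What to change.** Replace the urinalysis sentence in SAP 11.3 with: *Urinalysis results will be summarized by scheduled visit and treatment group (frequency and percentage for categorical dipstick results, descriptive statistics for continuous results) for the Safety Analysis Set; all data will also be listed.*

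A count, by arm, of subjects negative at baseline and positive post-dose for occult blood and erythrocytes would be a useful optional addition. It goes beyond what Protocol 10.3.3 asks for.

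If the sponsor prefers a listing only, SAP Section 5 should declare that as a change from the protocol and give the reason.

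The cost is a small amount of extra table programming. The samples are already scheduled and analyzed centrally, so no new data are needed and study conduct does not change.

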8.1.4 Biomarker Assessments

The proposed mechanism of action of CSL312 in IPF will be explored using biomarkers of coagulation, inflammation, alveolar epithelial cell damage, tissue modeling, and fibrosis, such as but not limited to, those detailed below.

The following biomarkers will be measured: pF1+2, fibrinogen, D-dimer, aPTT, high-sensitivity C-reactive protein (hs-CRP), and monocytes. Samples will be collected at Screening, before administration of the IV loading dose of investigational product on Day 1, and on Days 8, 36, 64 and 92. hs-CRP will be assessed at all study visits, including Screening, before administration of the IV loading dose investigational product and immediately after the EOI on Day 1.

The following biomarkers will be measured at Screening, before administration of the IV loading dose of investigational product on Day 1, and on Days 8, 36, 64, and 92: FXII (free vs. total), C3a, C5a, IL-8, IL-10, CCL-2, CXCL-1, CCL-18, PAI-1, surfactant protein A (SP-A), surfactant protein D (SP-D), YKL-40, tenascin-C (TN-C), thrombospondin-1 (TSP-1), VEGF, neo-epitope of matrix metalloproteinase-mediated degradation of citrullinated vimentin (VICM), neo-epitope of matrix metalloproteinase-mediated degradation of C-reactive protein (CRPM), pro-Fib, neo-epitope of calprotectin generated by human neutrophil elastase (CPa9-HNE), and collagen synthetic and degradation neo-epitopes (pro-C3/4/6 and C1/3/4/6M).

The following PD parameters and biomarkers will be assessed at all study visits at which PK is being assessed, including before administration of the IV loading dose of investigational product and immediately after the EOI on Day 1: FXIIa-mediated kallikrein activity, FXII concentration, IL-6, and hs-CRP. Additionally, hs-CRP will also be assessed at Screening.

Blood transcriptomics: Blood will be collected for RNA sequencing to investigate changes in gene expression at Screening, before administration of the IV loading dose of investigational product on Day 1, and on Days 8, 36, 64, and 92.

Proteomic analysis: Blood will be collected to characterize the plasma proteome at Screening, before administration of the IV loading dose of investigational product on Day 1, and on Days 8, 36, 64, and 92.

Details related to the collection, preparation, transfer, and storage of biomarker samples will be provided in the laboratory manual. Blood sampling time points for biomarker assessment are indicated in the [Schedule of Assessments](#).

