4.1 Objectives and Endpoints

The primary objective of this study is to investigate the safety of CSL312 in subjects with IPF.

The secondary objectives of the study are:

1. To characterize the systemic PK of CSL312 in patients with IPF.
2. To investigate the PD activity of CSL312 in patients with IPF.

The exploratory objectives of the study are:

1. To investigate the potential effect of CSL312 on FXII-related pathways in patients with IPF.
2. To investigate the effect of CSL312 on lung function in patients with IPF.

Table 1 Study Objectives and Endpoints

Objectives	Endpoints and /or Estimand	Summary Measure(s)
Primary	Subjects experiencing treatment-emergent adverse events (TEAEs) including: 
 • Serious adverse events (SAEs) • Adverse events of special interest (AESIs [bleeding events, thromboembolic events (TEE), severe hypersensitivity]) • CSL312-induced antidrug antibodies (ADAs) • Clinically significant abnormalities in laboratory assessments that are reported as adverse events (AEs) 	Number and proportion of subjects experiencing the specified safety events after treatment with IP (CSL312 or placebo)
Secondary		
1	Plasma PK parameters after SC administration of CSL312 at each SC dosing interval: 
 • Trough plasma concentration (C_{trough}) • Maximum plasma concentration (C_{max}) (last SC dosing interval only) • Time to reach maximum plasma concentration (T_{max}) (last SC dosing interval only) • Area under the plasma concentration-time curve after the first dose interval (AUC_{0-tau}) (last SC dosing interval only) 	
 • Mean (SD) and geometric mean (geometric percent coefficient of variation [geometric %CV]) for all PK parameters except for T_{max} • Median (minimum, maximum) for T_{max}

Objectives	Endpoints and /or Estimand	Summary Measure(s)
1	Plasma PK parameters after the IV dose of CSL312: 
 • C_{max} • T_{max} • C_{trough} 	
 • Mean (SD) and geometric mean (geometric %CV) for all PK parameters except for T_{max} • Median (minimum, maximum) for T_{max}
2	Effect of treatment with CSL312 on activated coagulation factor XII (FXIIa) mediated kallikrein activity	
 • Mean (SD) change from Baseline in FXIIa-mediated kallikrein activity by treatment • Mean percentage of Baseline in FXIIa-mediated kallikrein activity by treatment
Exploratory		

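### Laboratory shift tables use only the Day 92 (or last earlier) value, so on-treatment abnormalities that resolve are classed as not shifted, and no table counts them by arm

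*SAP*

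**What the plan says.** SAP section 4.1 states: "The primary objective of this study is to investigate the safety of CSL312 in subjects with IPF". SAP section 11.3 then sets out the laboratory outputs.

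- **Shift tables.** "For each of the hematology and serum biochemistry lab tests, shift tables will be constructed to compare the individual subject baseline value" "to their Day 92 (or last observed value prior to Day 92 in case of dropouts or missing assessment at Day 92) value", each classed against the normal range. Section 11.3 lists aPTT, PT/INR, pF1+2, fibrinogen and D-dimer under serum biochemistry, so these follow the same rule. Urinalysis is only listed.
- **By-visit summaries.** "Measured laboratory values will be summarized descriptively by scheduled visit", and changes from baseline are presented in the same way. SAP section 7 defines a continuous summary as including quartiles, minimum and maximum as well as mean and SD. SAP section 8.2.5 keeps unscheduled data out of by-visit summaries.
- **Listing.** "A by-subject listing of all laboratory values including flag for values out of normal range will be provided"; it covers scheduled and unscheduled visits.

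No shift to a worst value, no shift by visit and no count of subjects abnormal at any time is planned. The remark in section 11.3 about percentages at a scheduled visit sets a denominator and does not define a further shift table. In the same section, positive immunogenicity tests are counted at any time as well as at Day 36 and Day 92.

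**The concern.** A shift table is the output that shows, arm against arm, how many subjects crossed the reference range. Here it uses one post-baseline value per subject. A subject whose result became abnormal at Day 8, 36 or 64 and recovered by Day 92 appears in the same cell as a subject who was never abnormal.

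The rule also treats like cases differently. If the abnormal result happens to be the last one available, because the subject left or the Day 92 sample is missing, the subject counts as shifted. If the subject stays and recovers, the same result disappears from the table. A difference between arms in the table can therefore reflect who stayed as well as who became abnormal.

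At stake is the descriptive laboratory safety comparison in a trial whose primary objective is safety.

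**Working it through.** **1. Group size.** The documents give no laboratory abnormality rates, so the only design figure to reproduce is enrollment (SAP section 4.4): 70 / 0.88 = 79.5, rounded up to 80; 35 / 0.88 = 39.8, rounded up to 40 per arm. Both match the plan. I use 40 per arm below and take all draws as complete.

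**2. Draws available and used.** In the protocol's Schedule of Assessments, the central hematology, biochemistry and coagulation row is marked at Screening, Day 1, the three SC dosing visits and the end-of-treatment visit. The table's layout is broken in the text available to me, but protocol section 8.1.4 gives the same days for the coagulation, hs-CRP and monocyte samples: "on Day 1, and on Days 8, 36, 64 and 92". That makes four post-baseline panels. A completer contributes one of them to the shift table, so 3/4 of the scheduled panels and all unscheduled draws are unused.

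**3. The rule applied to four subjects, all normal at baseline.**

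| Subject | Day 8 | Later panels | Shift table |
|---|---|---|---|
| A | normal | all normal | not shifted |
| B | abnormal | normal through Day 92 | not shifted |
| C | abnormal | none available | shifted |
| D | abnormal | abnormal through Day 92 | shifted |

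B and C have the same Day 8 finding and are classed differently.

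**4. Size, under assumed patterns.**

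*(a) Full persistence to Day 92.* Share missed = 0.

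*(b) One abnormal visit per affected subject, equally likely to be any of the four.* Let r be the proportion of subjects ever affected. Worst-value count = 40r; Day 92 count = 40r/4; share missed = 1 − 1/4 = 75%; chance that the Day 92 table shows no case = (1 − r/4)^40.

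| r | Worst-value count | Day 92 count | Chance of no case at Day 92 |
|---|---|---|---|
| 5% | 2 | 0.5 | 0.605 |
| 10% | 4 | 1 | 0.363 |
| 20% | 8 | 2 | 0.129 |

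*(c) Abnormality independent at each visit with probability p.* Ever abnormal = 1 − (1 − p)^4; share missed = 1 − p / [1 − (1 − p)^4].

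| p | Ever abnormal | Expected in 40 | Day 92 count | Share missed |
|---|---|---|---|---|
| 2% | 0.0776 | 3.1 | 0.8 | 74% |
| 5% | 0.1855 | 7.4 | 2 | 73% |
| 10% | 0.3439 | 13.8 | 4 | 71% |
| 20% | 0.5904 | 23.6 | 8 | 66% |

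**5. Timing of Day 92 relative to dosing.** SC doses fall on Days 8, 36 and 64 (protocol section 8.5.3). Intervals: 36 − 8 = 28, 64 − 36 = 28, 92 − 64 = 28 days. Day 92 is as far from the preceding SC dose as Days 36 and 64 are.

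**The case against.** The strongest reply is that nothing is hidden. The by-visit tables give each arm's minimum and maximum at each scheduled visit, so a single high ALT at Day 36 would be the Day 36 maximum in its arm. Every value, scheduled or not, is listed and flagged. Protocol section 9.1.1 requires clinically significant values or changes at any visit to be recorded as adverse events, and those are tabulated by arm. Increases in aPTT are exempt from that reporting, but aPTT has its own repeated-measures comparison at each time point (SAP sections 13.1 and 13.2). The IDMC receives laboratory listings. Protocol section 10.3.3 asks only for descriptive laboratory summaries by treatment group. Worst-value tables also collect noise: with an assumed 2.5% tail and independent draws, four looks give 1 − 0.975^4 = 9.6%, or about 3.9 of 40 subjects per test and direction, against 1 of 40 at Day 92 alone.

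Most of this stands, and it rules out several stronger readings that a reader might infer.

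- *That the primary endpoint is compromised.* It is not. Its laboratory component is clinically significant abnormalities reported as adverse events (SAP section 4.1), and it does not use the shift table.
- *That the by-visit output shows only means.* SAP section 7 includes minimum and maximum.
- *That Day 92 is a uniquely low-exposure sample.* Step 5 shows that Days 36 and 64 are equally far from the preceding SC dose.
- *That 75% of abnormalities will be lost.* That figure belongs to one assumed pattern. With an 18-day half-life and 4-weekly dosing (protocol section 3.3.2), persistence is quite possible.

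What remains is the missing count. A maximum shows one extreme value; it does not say how many subjects crossed the range or where they started, and it omits unscheduled draws. Listings are not tabulated by arm. Adverse event capture depends on investigator judgment. The aPTT model compares means. Persistence cannot be taken for granted either: in the sponsor's COVID-19 study, the related ALT and AST increases in one CSL312 subject resolved within a day of onset (protocol section 1.2.3.4).

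**Conclusion.** The point holds as a limited reporting defect. The planned shift tables class resolved on-treatment abnormalities as no shift, and class a subject with the same result as shifted if no later sample exists. No other planned table counts, by treatment group, the subjects out of range at any time on treatment.

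The size cannot be fixed from the documents. It is zero if abnormalities persist to Day 92, 66% to 74% under independence across visits at 2% to 20% per visit, and 75% if each abnormality occupies one scheduled visit chosen at random. These figures assume complete draws and normal baselines. The underlying data are collected and reported elsewhere, and the primary endpoint and the sample size are untouched. I would class this as a cheap improvement that is worth making.

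**What to change.** In SAP section 11.3, add shift tables by treatment group for each hematology, biochemistry and coagulation test: baseline category to the category of the highest post-baseline value, and separately to that of the lowest, over all scheduled and unscheduled on-treatment draws. State that unscheduled draws are included here as an exception to section 8.2.5. Keep the Day 92 shift as a second table, since it describes status at the end of the observation period.

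No new data are needed, and SAP section 3 leaves analysis decisions open until database lock. The cost is some programming and more random single excursions in both arms. The placebo arm is the reference for judging those, so the tables should be read as a between-arm comparison.
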